The QLQ-BR23 is a broadly used questionnaire that has been validated in Danish [34, 35]. The questionnaire includes several items of interest, but specifically for the present study, we focus on breast symptoms as a primary outcome. The remaining items from the questionnaire will be considered secondary outcomes, as described below. The QLQ-BR23 questionnaire will be filled out by the patients once weekly for the duration of the radiation therapy, and once weekly for three weeks after the last radiation fraction.

Secondary outcomes

The QLQ-C30 is a questionnaire concerning the quality of life in cancer patients in general, which is widely used and has been validated in Danish [36]. All items in the QLQ-C30 as well as the items from QLQ-BR23 (above) that are not mentioned under primary outcomes will be considered secondary outcomes. Patients will be asked to answer both questionnaires at baseline, once weekly during radiation therapy, and once weekly for three weeks after the last radiation fraction.

Patients will be asked about steroid cream usage for radiation dermatitis at baseline, once weekly during radiation therapy, and once weekly for three weeks after the last radiation fraction.

Demographic and background variables will be collected at baseline (see table 2 for a full list of demographic and background variables).

Participant timeline

The participant timeline is outlined in table 3. At the pre-screen consent, the patients will be informed that they have a right to 24 hours of consideration prior to deciding to participate in the trial or not. Oral and written consent will be obtained by the primary investigator at the time noted

in table 3, or at a maximum 24 hours hereafter. There will be no study-specific post-trial care for the participants, other than following the standard treatment regimens offered at Rigshospitalet.

Randomization and blinding

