This study will be conducted in compliance with the protocol, EU ICH-GCP guidelines and the applicable regulatory requirements. The standard procedures for quality control and quality assurance are followed in compliance with the ICH-GCP guideline, and investigator/sponsor allows direct access to data/documents for monitoring, auditing, and inspection from both Danish Medicines Agency and the Good Clinical Practice (GCP)-unit. The study will be audited by the GCP Unit of the University of Copenhagen. The GCP Unit will be independent from the investigators and sponsors, and have direct access to the electronic case report forms as well as the trial master file. The GCP Unit will also perform data monitoring. The GCP Unit is an independent unit that manages clinical trials in Denmark. Further information can be found at <http://www.gcp-enhed.dk>. No interim analyses have been planned. Currently, a monitoring schedule has not been formulated.

Harms

Adverse reactions to melatonin

Melatonin is non-toxic in both physiological and pharmacological doses [39]. In mice, rabbits, cats, and dogs, melatonin doses of 800 mg/kg, administered intravenously, have demonstrated no toxicity [40].

A study administered 1 g of melatonin orally to patients for 25-30 days, with drowsiness as the only adverse reaction [41]. These patients had substantial clinical tests (hematological and blood chemistry tests, urine analysis, heart rate and blood pressure monitoring and ECG) performed, and no reactions to melatonin were demonstrated [41]. Another study investigated the effect of intravenously administered melatonin in healthy subjects, as well as patients with Parkinson's disease and epilepsy. They applied 1.25 mg/kg melatonin as a bolus injection. One of the patients, who had 1.25 mg/kg melatonin intravenously, received further two doses of 0.5 mg/kg. Correspondingly, melatonin was non-toxic and no adverse reactions were observed [42].

Furthermore, melatonin has been used as an intravenous infusion in neonates with sepsis, in neonates undergoing abdominal surgery, and in preterm infants [43-45]. A total of 224 patients were included (of who 105 received melatonin) and no adverse reactions were reported, at a dose of 10 mg/kg intravenously [43-45].

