Melatonin has also been given in very large doses up to 100 mg intravenously in adults, with no adverse reactions [46]. Other studies investigated melatonin when used as a pre-medication for gynecological laparoscopic surgery, and demonstrated no adverse reactions at a dose of 5-20 mg of sublingual melatonin [47, 48]. No adverse reactions were reported in a study investigating pre-medication with 5 mg melatonin prior to laparoscopic cholecystectomy [49].

Drowsiness, confusion and depression has been described as side-effects of melatonin in a study examining if melatonin could augment antidepressant treatment in patients with depression [50]. Furthermore, a few studies report headache [51] and fatigue as side-effects of melatonin [52].

Adverse reactions to DMSO

Dimethyl sulfoxide (DMSO) is regularly used in the treatment of interstitial cystitis either as monotherapy, or serving as a vehicle for anti-inflammatory agents [27, 53-55]. DMSO has previously been applied as a solvent for intravesical drug administration in the treatment of bladder cancer [56]. An adverse reaction of DMSO is a garlic-like breath odor and taste, due to pulmonary elimination of a small percentage of the DMSO as dimethyl sulfide. One study demonstrated that up to 48% of patients with interstitial cystitis reported adverse reactions, including urethral irritation and nausea [53]. However, the dose in this study was a total of 25 g of DMSO (50 ml fluid of 500 mg DMSO/ml), which is a much higher dose than we aim to apply [53]. These adverse reactions are self-limiting, lasting up to 24-48 hours [27, 53, 54]. DMSO has demonstrated a self-limiting mild burning sensation as an adverse reaction when administered topically [57], but DMSO dose locally was approximately 50 times larger than in current study [57], and DMSO was applied every 8 hours, opposed to the current application two times a day [57].

Adverse events

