The subjects will be questioned about adverse events once weekly during treatment. An adverse event is defined as any medical event that leads to an unwanted effect in the subject after the administration of the intervention medication, without any necessary connection between the adverse event and the intervention. An adverse reaction is defined as harm or unwanted reaction to a drug, no matter the dosage. We have defined six pre-specified self-reported symptoms (nervousness, confusion, depressed mood, dizziness, headache, or garlic like odor), based on the most commonly reported adverse reactions of melatonin and DMSO available in the literature [41, 50-53]. Patients will also be asked to report additional symptoms of adverse effects, if any. Both adverse reactions and adverse events will be reported in the eCRF.

Serious adverse events (SAE) are defined as any medical effect that result in death, are life-threatening, lead to hospitalization, result in disability or permanent damage, or any other important medical event. All serious adverse events will be registered in EudraCT..

Serious adverse drug reactions (SARs) will be reported annually. Most likely this will not be applicable to this study, as it will last less than a year. In this case, SARs will be reported on conclusion of the study.

Sudden unexpected serious adverse reactions (SUSARs) will be reported immediately to the Danish Medicines Authority and the local ethics committee. Adverse event registration will commence on the first study day and be finalized after the last study day. In case of serious adverse reactions, the sponsor can decide if the study will be terminated. It is the sponsor's responsibility to evaluate if an adverse event is a SUSAR. SUSARs that are lethal or life-threatening will be registered and reported to the Danish Medicines Agency as fast as possible and at the latest 7 days after the sponsor has obtained knowledge of such an adverse event. All other SUSARs will be reported to the Danish Medicines Agency within 15 days. Due to not expecting any serious adverse reactions, all SARs will be considered unexpected and therefore considered SUSARs.

Ethical considerations

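### Drowsiness is the only reaction the Harms section gives for more than one of the references behind the symptom list, yet it is not among the six pre-specified symptoms

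*Combined protocol and SAP*

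**What the plan says.** Under Harms, Adverse events, the protocol schedules a weekly enquiry: "The subjects will be questioned about adverse events once weekly during treatment". It pre-specifies six symptoms for patients to report: "nervousness, confusion, depressed mood, dizziness, headache, or garlic like odor), based on the most commonly reported adverse reactions". The substances meant are melatonin and DMSO, and the source is given as reports "available in the literature [41, 50-53"]. An open request follows: "Patients will also be asked to report additional symptoms of adverse effects, if any". Events and reactions both go into the eCRF.

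Under Harms, Adverse reactions to melatonin, four of the same references are summarised as follows:

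- Reference 41: "A study administered 1 g of melatonin orally to patients for 25-30 days, with drowsiness as the only adverse reaction [41"]. The clinical tests done in that study are said to have shown no reactions.
- Reference 50: "Drowsiness, confusion and depression has been described as side-effects of melatonin", in a study of add-on treatment in depression.
- References 51 and 52: "a few studies report headache [51] and fatigue as side-effects of melatonin [52"].

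Under Adverse reactions to DMSO, urethral irritation and nausea are given for reference 53. The garlic-like odor is described in a sentence that carries no citation.

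**The concern.** A list said to rest on the commonest reactions in five named references should contain the reaction that the protocol most often attributes to those references. It does not. Reference 41 is cited as a basis for the list, but the one reaction the protocol reports from it is left out. From the sentence on reference 50 the list takes the second and third reactions and omits the first.

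What is at stake is the completeness of the tolerability record. The protocol calls the trial pivotal and expects that positive results could change practice. A statement on how well a melatonin cream is tolerated is weaker if the reaction its authors most often attribute to melatonin depended on patients raising it themselves.

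**Working it through.** No power or sample size calculation bears on this point. The check is a count and a comparison of the symptom list with the Harms summary.

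**Step 1. The stated count.** Nervousness, confusion, depressed mood, dizziness, headache and garlic-like odor make 6, which agrees with the protocol's figure of six.

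**Step 2. From the cited references to the list.**

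| Reference | Reaction given in the Harms section | On the list? |
|---|---|---|
| 41 | Drowsiness (only reaction) | No |
| 50 | Drowsiness | No |
| 50 | Confusion | Yes |
| 50 | Depression | Yes, as depressed mood |
| 51 | Headache | Yes |
| 52 | Fatigue | No |
| 53 | Urethral irritation, nausea (DMSO into the bladder) | No |

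Drowsiness is given for 2 of the 5 cited references. Every other reaction in the table is given for 1.

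**Step 3. From the list back to the references.**

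- Traceable to a cited reference: confusion (50), depressed mood (50), headache (51). That is 3.
- Described in the Harms section without a citation: garlic-like odor. That is 1.
- Attributed to no reference in the Harms section: nervousness, dizziness. That is 2.

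The total is 3 + 1 + 2 = 6. Reference 41 contributes no item.

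**Step 4. Routes by which drowsiness could still be recorded.** The open request for additional symptoms is one. The other candidate is the QLQ-C30, which patients answer at baseline, weekly during radiation therapy and weekly for three weeks afterwards. Its answers are secondary outcomes ("All items in the QLQ-C30 as well as the items from QLQ-BR23 (above" not named as primary). The protocol does not list the questionnaire's items and nowhere says that its answers enter the adverse-event record. Only the open request can therefore be counted on.

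**Step 5. Burden of one more named symptom.** Table 3 marks adverse-event monitoring in all 12 of its columns, from screening to the third follow-up week. One added symptom therefore means at most 1 × 12 = 12 further questions per patient. The list becomes 6 + 1 = 7 items, or stays at 6 if drowsiness replaces dizziness.

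**The case against.** The strongest reply is that nothing is lost. Patients are questioned weekly, are invited to mention anything else, and all events are recorded. This stands to the extent that drowsiness is not excluded from collection. A reader might infer that the trial would miss drowsiness altogether, and the open request rules that out. What remains is the difference between a symptom that is prompted and one that is not. Even this rests on an inference: the protocol does not say in so many words that each of the six is asked by name, although a separate request for additional symptoms implies it.

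A second reply is that choosing symptoms is a matter of judgement. Nausea and urethral irritation, given for reference 53, are also off the list, and route and dose may explain that. The Harms section also reports high intravenous and sublingual melatonin doses without adverse reactions, which weakens any expectation of drowsiness from a cream. This is fair, and it is why the omission of every reaction in the summary should not be read as an error. But the protocol gives no such reason for drowsiness. The same argument would apply to confusion and depressed mood, which come from the same reference 50 and were kept.

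A third reply is that the cited papers may support the list as it is. They were not available, so the point concerns only what the protocol says of them. If they do support the list, the Harms summary needs correcting, and the two parts must still be reconciled.

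It is also tempting to read dizziness as a slip for drowsiness. Dizziness has no source in the Harms section, which fits a slip, but neither has nervousness. The documents cannot settle it.

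**Conclusion.** The mismatch is established from the protocol's own text: the list does not follow from its stated basis, and the best-supported reaction is the one missing. The consequence is minor. Unprompted, drowsiness may be captured less completely than the six listed symptoms. The Harms section gives no frequency for drowsiness and the protocol gives no reporting rates, so the size of any loss cannot be derived.

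A reader might go further and infer that the trial's main conclusions, or the comparison of adverse events between the arms, are distorted. The documents do not support that. None of the three primary outcomes (RTOG score, image analysis, QLQ-BR23 breast symptoms) uses the symptom list, and there are no figures from which an effect on the comparison of adverse events could be shown.

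The conclusion rests on two assumptions: that the six symptoms are prompted and others are not, and that the Harms section summarises its references accurately.

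**What to change.** Before the trial starts, reconcile the symptom list under Adverse events with the summaries under Adverse reactions to melatonin and to DMSO. Include drowsiness among the named symptoms in the protocol and on the eCRF form, as a seventh item, or in place of dizziness if the authors confirm that dizziness was a slip. In the same edit, state where nervousness comes from, and dizziness if it is kept.

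The cost is one sentence of the protocol and one eCRF form. For patients it is at most one more question at each adverse-event check already scheduled, up to 12 per patient by Table 3. No visit is added.

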Connective tissue diseases	Patient
Disease and treatment	Source
Tumor type	Pathology report
Tumor size	Surgical report
Location of tumor	Surgical report
Lymph node status	Pathology report
Metastases	Electronic health record
Axillary dissection	Surgical report
Chemotherapy prior to radiation	Electronic health record
Type of chemotherapy	Electronic health record
Radiation dosage	Radiation treatment plan
Hypo-/hyperfractioning of radiation therapy	Radiation treatment plan

¹Central Person Register in Denmark. ²Fitzpatrick scale.

Table 3: Participant timeline

Activity/assessment	Pre-study screening/consent	Pre-study baseline/randomization	First radiation fraction	Study visit week 1	Study visit week 2	Study visit week 3	Study visit week 4	Study visit week 5	Last radiation fraction	Follow-up week 1	Follow-up week 2	Follow-up week 3
Prescreening consent	●											
Screening log	●											
Consent form	●											
Inclusion/exclusion form	●											
Randomization		●										
Demographics questionnaire		●										
Instruction in application of cream		●										
Handover of drug/placebo ^a	●			●			●					
Evaluation of compliance			●	●	●	●	●	●	●			
RTOG score evaluation ^b		●	●	●	●	●	●	●	●	●	●	●
Clinical photography	●	●	●	●	●	●	●	●	●	●	●	●
QLQ-C30 ^c	●	●	●	●	●	●	●	●	●	●	●	●
QLQ-BR23 ^c	●	●	●	●	●	●	●	●	●	●	●	●
Steroid usage evaluation	●	●	●	●	●	●	●	●	●	●	●	●
Monitoring of adverse events	●	●	●	●	●	●	●	●	●	●	●	●
Serious adverse event form ^d												
Conclusion of participation										●		

^a Patients will receive extra trial drug/placebo when required throughout study, therefore, the marked visits might vary from patient to patient depending on compliance. ^b RTOG score = Radiation Therapy Oncology Group cooperative group common toxicity criteria. ^c QLQ-C30 and QLQ-BR23 =European Organization for Research and Treatment of Cancer quality of life questionnaires. ^d Serious Adverse event form will be filled in as needed throughout the trial.
